### ***6.1.3 Clinic Visits (Months 3 and 6)***

In order to reduce the burden of research visits and data collection, in-person visits in the e-Health arm and the standard care arm will coincide as much as possible with patients' routine clinic visits. Participants will be asked to complete a 4-day food record prior to each in-person clinic visit. At the visit, the Registered Dietitian will meet with participants in the in-person arm and will verify compliance with the prescribed diet. Participants will review the dietary goals and recommendations with participants and make adjustments as needed based upon observed weight loss. All participants will be rescreened for dysphagia using the MGH-SST and participants with dysphagia will be referred to a SLP before continuing in the study. If the SLP determines that a modification of their current diet is required, those modifications will be incorporated into the dietary recommendations. If the SLP determines that the participant cannot swallow safely, their study diet will be temporarily suspended until they can obtain a feeding tube. If they decline the feeding tube, participants will still be asked to complete the final visit by telephone and to consent for long term follow-up for survival. Participants' blood will also be drawn for research and safety laboratory studies.

### ***6.1.4 Treatment Withdrawals and Loss to Follow-up***

A subject has the right to refuse counseling sessions and contact from the RD at any time and for any reason. If participants express unwillingness to continue to participate in the trial, participants will be asked if they would be willing to be followed for telephone-based questionnaires, QOL and survival only, with a final telephone visit at 6 months. The treating RD or research coordinator will document the reasons for discontinuation in the EDC. Long-term follow-up for survival will continue until the end of the study and be included in the intention-to-treat analysis. For the primary safety analysis, telephone visits will be used to document adverse events, changes in medical history and medications. All attempts will be made to follow these subjects for all outcome measures by telephone if necessary. The analysis of data from subjects who stopped treatment and/or refused study visits is discussed in the data analysis section.

### **6.1.5 Final Evaluations and Post-Intervention Phone Calls**

The final visit will coincide with the participant's routine clinic visit approximately 6 months after study initiation. Weight, appetite, QOL and disease-specific questionnaires will be measured. Participants will return the study iPad at this visit and all participant data will be deleted from the iPad. Participants' blood will be drawn for research and safety laboratory studies, including a urine pregnancy test if participants have consented for the optional DXA study.

One month after the final clinic visit, the research coordinator will contact all participants by telephone to document adverse events. The research coordinator will also contact subjects approximately every 6 months until all participants have finished the study, to document vital status and weight, dates of feeding tube placement, tracheotomy or death.

### **6.1.6 End of Study Phone Call**

All participants will be contacted at the time of the last subject last visit in order to obtain vital status and dates of feeding tube placement, tracheotomy or death.

## **6.2 Definitions of Evaluations and Outcome Measures**

### **6.2.1 Primary Outcome Measures**

#### **6.2.1.1 Safety and Tolerability**

Safety will be evaluated using reporting of hospitalizations, deaths and other serious adverse events, and treatment discontinuations due to adverse events. Tolerability will be defined as the number of participants who do not decline nutritional counseling, i.e. the number of participants who complete the 6 months of counseling sessions in the in-person arm, or who enter at least 80% of the required data in the e-Health application arm. Tolerability will not be defined based on compliance with nutritional recommendations as compliance may be affected by other factors such as disease progression.

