## **8. Intervention Suspension Related to Nutritional Counseling**

While we do not anticipate serious adverse events from medical nutrition therapy, we will suspend the nutritional interventions while participants are hospitalized, or if participants withdraw consent during the study. If participants wish to continue in the study after discharge, they may resume nutritional counseling with the approval of their treating physician. If participants develop significant dysphagia during the study and are deemed unable to swallow safely by a Speech Language Pathologist, even with dietary modifications, the study nutritional goals will be suspended until participants are able to obtain a feeding tube. Participants who receive a feeding tube will then receive Jevity 1.5 at 1.5 times their estimated total daily energy expenditure, regardless of the study arm to which they have been randomized.

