### **9.1 *Safety and Tolerability***

All randomized subjects will be considered evaluable for tolerability and safety. Subjects lost to follow-up will be considered treatment failures at the time they drop out of the study. The data will be reviewed by the independent Medical Monitor, using the considerations here as guidelines. Their recommendation would then be reviewed by the Principal Investigator.

Safety data will be summarized by disease group and treatment group and reported to the independent Medical Monitor every 3 months during the study. Total numbers of adverse events will be compared within each disease group and among treatment groups using negative binomial regression and the proportion of participants experiencing each type of event by Fisher's exact test. Every 3 months the Medical Monitor will review cumulative study reports to determine if there has been an excess rate of serious adverse events in any of the arms. At two interim analyses, mortality rates will be compared, and one or both intervention arms may be terminated for one or more disease groups according to pre-determined stopping rules described below.

In the tolerability analyses, a subject will be regarded as a treatment success if he/she complies with at least 80% of the nutritional counseling sessions, or enters at least 80% of the required electronic data.

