### **9.3 *Sample size calculation:***

Using the component estimates from weight data collected in the clinical trial of Ceftriaxone in ALS [13] the effective standard deviation for rate of change in weight assuming weight assessments every 2 weeks, an annual 23% mortality rate, and 20% loss to follow-up is 0.98 kg/month. Given a sample size of approximately 150 ALS participants randomized 1:1:1 to the two interventions and standard care will provide at least 80% power to detect a true 0.75-kg/month difference between each intervention arm and the control arm over 24 wks at a two-tailed  $p < 0.027$  using Dunnett's method (testing superiority of each intervention over standard care). Based on a non-inferiority bound of 0.5 kg/month, the study will have at least 80% power to declare the e-Health intervention non-inferior to in-person consultation with an RD based on a one-tailed test at  $p < 0.05$  and assuming that the two interventions are in fact equivalent.

**Accrual Targets:** We intend to enroll 3-4 ALS subjects per week for the first 12 weeks, after which the rate will slow to 2-3 subjects/week, in order to accommodate return schedules and telephone visits. It should take approximately 12 months to enroll 150 participants at an average rate of 10 subjects per month. PD and HD subjects will be enrolled separately based upon funding and infrastructure availability.

**Treatment Discontinuation Rate Targets:** Subjects who discontinue treatment will be considered treatment failures in the tolerability analysis. However if there is an elevated discontinuation or study drop-out rate, it will reduce the power to detect a significant treatment difference for the primary outcome. The Steering Committee will analyze enrollment and discontinuation rates at pre-specified intervals and if it appears that fewer than 25 subjects per arm will complete the 6 month study, they may recommend increasing the enrollment times or stopping early for futility.

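### Tolerability is defined as not declining counseling but scored on completion, with no rule for deaths; about 9-12% of each ALS intervention arm would fail through death alone

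*Protocol*

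**What the plan says.** Three places define tolerability, and they differ.

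- **Protocol 6.2.1.1 (primary outcome measures).** The in-person arm is scored on "the number of participants who do not decline nutritional counseling, i.e. the number of participants who complete the 6 months of counseling sessions". The e-Health arm is scored on participants "who enter at least 80% of the required data in the e-Health application arm". The section adds: "Tolerability will not be defined based on compliance with nutritional recommendations as compliance may be affected by other factors such as disease progression".
- **Protocol 9.1 (repeated in the Précis).** A participant is a success who "complies with at least 80% of the nutritional counseling sessions, or enters at least 80% of the required electronic data". So the in-person threshold is 80% here, but full completion in 6.2.1.1. The denominator is stated: "All randomized subjects will be considered evaluable for tolerability and safety". Loss to follow-up counts as failure, and section 9.3 says the same of anyone who discontinues treatment, with no exception by reason.
- **SAP, tolerability paragraph.** There is no success or failure score. Tolerability is the number of interactions with a dietitian or the app, and the time to the last interaction with a dietitian.

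On suspensions, section 8 states "we will suspend the nutritional interventions while participants are hospitalized". For an unsafe swallow, section 8 suspends the nutritional goals and section 6.1.3 the study diet, pending a feeding tube. Section 9.3 plans the ALS sample on "an annual 23% mortality rate".

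**The concern.** The concept in 6.2.1.1 is refusal: did the participant turn the counseling down? The score is completion. The two agree only if nobody stops for a reason other than refusal, which cannot be assumed in ALS over six months.

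Take an in-person participant who attends every session and dies at month 4. That person completed 4/6 = 67% of the period, so fails the completion rule in 6.2.1.1, and fails the 80% rule in 9.1 if sessions are counted over the full six months. By the stated concept the same person is a success. The protocol's reason for leaving dietary compliance out, that disease progression may affect it, applies equally to completing sessions and entering data.

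At stake is what a primary outcome means. A reader of the tolerability rate could not separate people who rejected the intervention from people who died while using it. The two scored arms are also held to different thresholds in 6.2.1.1, so the comparison between them is uneven before any data arrive.

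**Working it through.** The documents give no tolerability rate, target or power, so there is no stated figure to reproduce. The check asks what share of an ALS intervention arm would be scored as failing through death alone.

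**Inputs.** Mortality 23% per year and loss to follow-up 20%, period not stated (9.3). Intervention duration 6 months (3.1). 150 ALS participants randomized 1:1:1, so about 50 per arm (9.3). App entries every 2 weeks (5.1.2), so 13 cycles in 26 weeks.

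**Share dying by time t (years), constant hazard:** 1 - (1 - 0.23)^t.

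| Rule | t | Constant hazard | Linear, 0.23 × t | Of 50 (constant hazard) |
|---|---|---|---|---|
| Complete 6 months | 0.5 | 1 - 0.77^0.5 = 12.25% | 11.5% | 6.1 |
| 80% of 6 months (4.8 months) | 0.4 | 1 - 0.77^0.4 = 9.93% | 9.2% | 5.0 |
| 11 of 13 entries (week 22) | 22/52 | 10.47% | 9.7% | 5.2 |

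The third row arises because 80% of 13 is 10.4, so 11 entries are needed.

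**Allowing for loss to follow-up first.** With hazards λ = -ln 0.77 for death and μ for loss, the share dying before any loss is λ/(λ + μ) × (1 - exp(-(λ + μ)t)).

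- 20% loss per year: 9.5% at t = 0.4 and 11.6% at t = 0.5.
- 20% loss per 6 months: 9.1% at t = 0.4 and 11.0% at t = 0.5.

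Across rules and variants the share is about 9-12%, or roughly 5 to 6 of 50.

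**Unequal thresholds in 6.2.1.1.** At equal mortality and otherwise full engagement, 12.25% of the in-person arm fails through death. In the e-Health arm it is 9.93% (80% of elapsed time) or 10.47% (11 of 13 entries). The gap is 12.25 - 9.93 = 2.3 points or 12.25 - 10.47 = 1.8 points: about 2 points, or one participant in 50, against the in-person arm.

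**Suspended periods.** Under an 80% rule a participant can miss 13 - 11 = 2 of 13 two-week cycles. With contacts every 4 weeks (about 6 in all), 80% of 6 is 4.8, so 5 are needed and 1 can be missed. Short suspensions therefore need not cause failure. Three missed cycles would (10/13 = 77%), but only if entries are still required during a suspension, which no section says.

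**SAP measures.** A death at month 4 caps time to last interaction at 4 months and leaves at most 8 complete two-week cycles of the 13 (13 × 4/6 = 8.7). Both measures fall, with no refusal. No failure rate can be derived from them.

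**The case against.** The strongest reply is that the SAP has superseded the binary rule. It contains no completion criterion and no 80% threshold, so the 9-12% corresponds to nothing the SAP would report. That is right as far as it goes, but the SAP does not say how death enters its two measures either, and the protocol's rules remain in three places.

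A second reply is that completion is a legitimate notion of tolerability: section 2.1.7 describes the predecessor trial's completion difference in those terms. It is also fair that the disease-progression sentence in 6.2.1.1 explains only why dietary compliance is left out and does not promise to keep mortality out of completion. Both stand. They do not remove the mismatch, because 6.2.1.1 itself names not declining as the concept.

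A reader might infer more than the documents support:

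- **That protocol-ordered suspensions count as intolerance.** Only hospitalization expressly suspends the interventions. The swallowing rule names the diet or goals, not sessions or app entries, and required data are never defined. The documents are silent, and 80% absorbs short gaps.
- **That every ALS arm is affected.** Standard care has no tolerability criterion.
- **That mortality would create a spurious difference of about 6 points.** This needs one scored arm to have half the hazard of the other: 1 - 0.77^0.25 = 6.3% against 12.25%. Both scored arms share the same nutritional goals (5.1.2), and nothing in the documents supports such a contrast. Section 9.1 also specifies no between-arm test of tolerability.

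**Conclusion.** The point holds in this form. The protocol defines a primary outcome as not declining counseling, scores it on completion or data entry, uses two thresholds for the in-person arm, and leaves the scoring of death unstated. Followed as written, its rules would class about 9-12% of each ALS intervention arm (5 to 6 of 50) as failures through death alone. Section 6.2.1.1 would also place the in-person arm about 2 points lower at equal mortality. Under the SAP the same gap in the rules shortens time to last interaction and lowers the counts, by an amount that cannot be given as a failure rate.

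The size rests on the 23% planning value, a roughly constant hazard, otherwise full engagement, and sessions or entries spread evenly over six months. The last is only approximate in the in-person arm, where contacts run every 2-4 weeks as needed (6.1.2). Mortality in participants selected by the swallow screen is not given, and there is no planning mortality for PD or HD, so the figure applies to ALS only.

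**What to change.** Reconcile Protocol 6.2.1.1, 9.1, the Précis and the SAP to one definition.

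- Use the same 80% threshold in both intervention arms. Limit the denominator to sessions or app entries due while the participant was alive and the intervention was not suspended. State what counts as a due session in the in-person arm, since contact frequency varies.
- Count refusal, withdrawal from counseling and loss to follow-up as failures.
- Tabulate death, permanent assisted ventilation and suspension separately by arm.
- In the SAP, express interaction counts relative to time alive, and say whether death is a competing or a censoring event for time to last interaction.
- Keep the present rule as a sensitivity analysis.

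The cost is wording and one derivation. Death dates are already collected (6.1.5, 6.1.6) and hospitalizations reported (6.2.1.1). No section says that suspension start and stop dates are recorded, so they may have to be derived from adverse event dates (10.5.1) and disposition records. There is one real downside: a participant who dies early after good engagement, even in week 3 after one on-time entry, counts as a success. The tolerability rate must therefore be read beside the death table. No clinical rule changes.

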#### **Adverse Events:**

The research coordinator will collect data by telephone on adverse events after the first month, and at each clinic visit in all participants. Adverse events will be recorded using the MedDRA coding system. Safety labs including the basic metabolic panel, lipid profile, hemoglobin A1c and liver function tests will be performed at the Screening/Baseline and routine clinic visits.

#### **6.2.1.2 Primary Outcome Measure: Weight**

The primary outcome of weight will be compared between each intervention arm and the control arm using the measured weights from each clinic visit, approximately every 3 months. Participants will be weight lightly clothed without shoes or braces. Participants may use a chair scale or wheelchair scale if they are unable to stand. Body mass index will be calculated at the initial visit using a baseline height measurement.

Weight will also be used to direct therapy. Participants in the in-person counseling arm will be given a Self-Weighing Log to weigh themselves every 2-4 weeks, and to call the center if they experience 2 or more pounds of weight loss compared to their baseline weight. The e-Health arm will be prompted automatically by the application to weigh themselves twice every 2 weeks, and to enter the data into the application. If there is a greater than 2 pound change from the prior weight, the treating RD will be alerted and will be able to contact the participant by telephone or by instant messaging through the application to verify the weight change. They will then be able to make dietary adjustments and to monitor weights more frequently in any participant who experiences weight loss. Self-reported weights will be verified at routine clinic visits. Self-reported weights will also be used to compare the two intervention arms.

### ***6.2.2 Secondary Outcome Measures:***

In order to monitor dietary compliance and to collect comprehensive nutritional information, we will use 4 day food records in the in-person counseling arm. The e-Health application arm will be prompted every 2 weeks to report all dietary intake for 4 days (including 1 weekend day) along with their activity level and home weights (measured twice over 2 days). The 4 day food records will be analyzed using Nutrition Data System for Research (NDSR) software Version 2014 by the RD and coordinator, while the e-Health application data will automatically analyze the data into total caloric intake, percent protein, fat, and carbohydrate.

### ***6.2.3 Tertiary Outcome Measures:***

Tertiary outcome measures will be collected by a research coordinator at every clinic visit, approximately every 3 months, including standard care participants. Tertiary outcome measures will include change in disease-related questionnaires (ALSFRS-R, UDysRS, UHDRS), quality of life using the PROMIS SF v1.1 questionnaire, and the CNAQ appetite questionnaire. For participants who are unable to physically come to the clinic for their clinic visits, the patient-reported sections of these questionnaires will be administered by telephone. The study is not powered to detect changes in disease progression.

#### ***6.2.3.1 Survival:***

Survival will be defined as time to death, tracheotomy or the initiation of permanent assisted ventilation (PAV). PAV is defined as noninvasive or invasive ventilation used for more than 22 hours in a 24-hour period for 14 consecutive days. Participants will also be asked to consent for long-term follow-up at the initial visit and their vital status will be determined every six months by telephone until the final participant completes the study, unless they expressly withdraw their consent.

#### ***6.2.3.2 Time to Percutaneous Endoscopic Gastrostomy (PEG) or Jejunostomy (PEJ) Placement:***

Date of placement of PEG or PEJ feeding tubes will be captured using the EDC. Frequency and time to placement of feeding tubes will be compared between the different arms. We hypothesize that participants in the two intervention arms will be more willing to undergo

feeding tube placement and that there will be less weight loss before feeding tube placement in the two intervention arms.

### **6.2.3.3 Exploratory Outcome Measures:**

Exploratory outcome measures include changes in weight, fat mass, and fat free mass using DXA scans, lipid levels, serum markers of nutritional status, and the appetite regulatory hormones Leptin, Ghrelin and PYY. Leptin is an important regulator of appetite, food intake, and energy expenditure (reviewed in [40]). Leptin is a peripherally circulating hormone produced by adipose tissue which crosses the blood brain barrier and binds to leptin receptors primarily in the hypothalamus where it leads to anorexia and weight loss. In addition to regulating appetite, leptin has also been reported to be neuroprotective in ischemic models and amyloid toxicity [41-43]. Patients with Alzheimer's disease have been shown to have lower circulating leptin levels than controls, and low premorbid leptin levels are associated with an increased risk of cognitive decline and Alzheimer's disease in two large prospective studies, even adjusted for waist-hip ratio and BMI [44, 45]. This is in contrast to the data showing that mid-life obesity is a risk factor for Alzheimer's disease. Leptin levels have not been measured in ALS except in one small study of 21 patients where the results were not compared to controls and not adjusted for BMI [46].

## **7. Adverse Experiences Related to Medical Nutrition Therapy**

### ***Weight gain***

An increase in weight in either of the intervention arms is expected and would not be considered an adverse event. In the High-Fat/High Calorie versus Optimal Nutrition in ALS clinical trial, there were no complications of heart disease, diabetes, or breathing problems in the study arms who received hypercaloric diets. Increase in weight was seen in the high-carbohydrate hypercaloric arm and was associated with fewer AE and SAE. We will therefore tell participants that they are expected to gain weight and that we will not consider this an adverse event.

### ***Gastrointestinal Side Effects***

In the High-Fat/High Calorie clinical trial, the following adverse events were observed (Table 3). The most common adverse events were gastrointestinal and presumably related to the enteral formulae that participants received. Because the current study is designed primarily for participants taking food by mouth, we anticipate a lower frequency of gastrointestinal side effects. However, we anticipate the following common adverse events that may be observed with any nutritional intervention:

- Abdominal Fullness
- Belching
- Flatulence
- Constipation
- Heartburn

